8.3.3.3 EXPECTEDNESS

The study clinician and the principle investigator in consultation will be responsible for determining whether an adverse event (AE) is expected or unexpected. An AE will be considered unexpected if the nature, severity, or frequency of the event is not consistent with the risk information previously described for the study intervention.

8.3.4 TIME PERIOD AND FREQUENCY FOR EVENT ASSESSMENT AND FOLLOW-UP

The occurrence of an adverse event (AE) or serious adverse event (SAE) may come to the attention of study personnel during study visits and interviews of a study participant presenting for medical care, or upon review by a study monitor.

All AEs including local and systemic reactions not meeting the criteria for SAEs will be captured on the case report form (CRF). Information to be collected includes event description, time of onset, clinician's assessment of severity, relationship to study product (assessed by the study clinician), and time of resolution/stabilization of the event. All AEs occurring while on study must be documented appropriately regardless of relationship. All AEs will be followed to adequate resolution.

Any medical condition that is present at the time that the participant is screened will be considered as baseline and not reported as an AE. However, if the study participant's condition deteriorates at any time during the study, it will be recorded as an AE.

Changes in the severity of an AE will be documented to allow an assessment of the duration of the event at each level of severity to be performed. AEs characterized as intermittent require documentation of onset and duration of each episode.

The study principle investigator and either of the research assistants will record all reportable events with start dates occurring any time after informed consent is obtained until 7 (for non-serious AEs) or 30 days (for SAEs) after the last day of study participation. At each study visit, the investigator will inquire about the occurrence of AE/SAEs since the last visit. Events will be followed for outcome information until resolution or stabilization.

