All participants will be treated with respect, and we will be considerate of the time and energy that is involved with participation in this study. Participant retention will begin with the recruitment process. Based on medical records and release of information consent forms from the treating physician, only those patients who do not actively opt out will be contacted by phone to receive follow-up information about the study and assess their interest in participating. Once enrolled in the study, all participants will have contact with the study team at each measurement time point (baseline, 6 weeks and 12 weeks). In addition, based on group randomization the participants will also have contact with the study team either two times a week for six weeks or once a week for six weeks. Based on our prior experience, this level of contact helps to keep participants engaged. Calls to participants will also be scheduled at times that are preferred and convenient for each participant. We will also use telephone calls to remind participants about all in-person study visits. Participants not assigned to patient intervention arm will be

asked to complete 3 in-person educational sessions as well as three online training modules over the 6 week intervention period. This will encourage continued participation from patients assigned to this arm. Also, the importance of compliance will be emphasized throughout the study. Participants who do decide to withdraw from study participation however, will be encouraged to complete the study assessments. The reason for any missed intervention sessions as well as assessment sessions will be recorded for future analysis in order to improve planning for subsequent clinical trials.

All successful and unsuccessful attempts to contact participants will be documented within the subjects study record. Additionally, alternate contact numbers will be requested from participants to aide in locating the subject.

Participant recruitment and retention statistics will be collected and monitored on a regular basis such that any problems or negative trends can be identified early and appropriate measures taken and/or procedures modified.

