6 STUDY INTERVENTION

6.1 STUDY INTERVENTION(S) ADMINISTRATION

6.1.1 STUDY INTERVENTION DESCRIPTION

This will be a randomized controlled Phase 1, pilot clinical trial. Patients will be assigned to one of two study arms: 1) Biofeedback Intervention, 2) Attention Control. All participants in the study will continue with any other usual medical care they receive for their ACL reconstruction.

BIOFEEDBACK INTERVENTION

The 6-week biofeedback training program is focused on altering loading and movement asymmetry during biweekly sessions on non-consecutive days (12 sessions). The biofeedback training program will provide sensory (visual and tactile) feedback to the subject to heighten awareness of asymmetrical movement strategies (e.g. load shift, movement asymmetry) during a squat. The two exercises that will be completed during the biofeedback training program will be a visual feedback squat and a resisted squat (tactile feedback). Each of these tasks will be completed 30 (3 sets of 10 repetitions) times per session. We will provide a 20 second rest between trials, and a 10 minute break between the visual and tactile feedback exercises to decrease the effect of fatigue. Prior to the biofeedback intervention session, each participant will complete a 5-minute warmup on a stationary bike as was described during the biomechanical assessments.

Visual feedback: The simplest way to provide biofeedback during a squat is through visual feedback of load. Under this approach, subjects are asked to stand on force plates, which measure the ground reaction forces (load) beneath each foot. Shoulder width for each participant will be measured as the distance between acromioclavicular joints. This distance will then be measured on the force plates and 2 pieces of tape will be placed this distance apart (one on each force plate) and participants will be asked to stand with one heel on each piece of tape. Stance width will be recorded on the data collection sheet and then entered into REDCap so that this distance can be used during each subsequent training and testing session and foot position can be measured and marked prior to participant arrival. Participants face a projection screen that displays two bar graphs of the vertical ground reaction force, depicting each foot's

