Tactile feedback: The second set of exercises at each biofeedback session will be resisted squats. A subject will be asked to squat while an external force is applied to the side of the knee (Figure 3) requiring the subject to work against this resistance to maintain balance and complete the squat. The band will be placed on the surgical limb of each patient and will be pulled at approximately a 45 degree angle toward the contralateral side. Pulling the subject toward the non-operative limb (one that is typically displaying higher loads) will require the subject to pull toward the surgical limb and maintain good frontal plane position by resisting frontal plane valgus. This is a typical exercise utilized in the clinic to aid in equal weight bearing and active hip abduction. The squat position that will be used during these exercises will be the same as the squat position used in both the visual biofeedback task as well as during the biomechanical testing. The subjects will be asked to stand with their feet at the standardized width and again squat until they make contact with the stool that will be positioned behind them during the biofeedback session. Subjects will be asked to complete 30 tactile feedback squats (3 sets of 10 squats) during each of the biofeedback sessions.

ATTENTION CONTROL

The 6-week attention control group program will focus on providing educational information to the participants related to the clinical and sports expectations as they are released to return to sport. These participants will be asked to meet 6 times during the 6-week intervention time period. Three of these visits will be completed in person and three will be completed using an online educational module (6 sessions). The online sessions will be completed in week 1, week 3, and week 5 while the in person sessions will be completed during week 2, week 4, and week 6. The content of these sessions will focus on providing information on ACL reconstruction, athlete expectation as they return to sport, incidence and risk factors for secondary ACL injuries, as well as some suggestions on the gradual progression back into sport.

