8.3.5 ADVERSE EVENT REPORTING

All AEs are collected, analyzed, and monitored by using an Adverse Event Form (MOOP Appendix G). AEs and/or laboratory abnormalities identified in the protocol as critical to participant safety will be reported to the NIAMS and the safety officer. All AEs experienced by a participant during the time frame specified in the protocol (from the initial day of testing as well as the initiation of the biofeedback program through the end of the study) will be reported, as outlined in the protocol (Section 1a of the MOOP).

The procedure for collecting and reporting AEs will be detailed in the following sections. This information will include the role of the Principal Investigator and the Medical Monitor ([name]) in assigning severity and defining the relationship between the AE and the study intervention. A sample AE form can be found in Appendix G. Requirements for reporting AEs to the NIAMS and the study's independent Safety Officer (SO)) is described below.

The Principal Investigator (PI) and study staff members will be responsible for the safety of study participants. It is not anticipated that there will be any significant physical or psychological risks associated with this study. However, federal regulations require prompt reporting to the Virginia Tech Institutional Review Board (IRB), all injuries, adverse events, or other unanticipated problems involving risks to subjects or others that occur in the course of a subject's participation in this research study.

Study team members who become aware of any adverse event related to the study will notify the principal investigator, [name], immediately. Study team members will have contact information for [name] for daytime, evening and weekend hours. If [name] is not available for contact when a study team member becomes aware of a study-related adverse event, [name] or [name], co-investigators on the study, will be contacted. Once [name] (or a co-investigator) is contacted about the adverse event, she / he will make a determination about the reporting requirements in accordance with the Virginia Tech IRB guidelines. This will include notification of the Virginia Tech IRB within 24-hours if a study-related death, within 5 business days if another serious adverse event, and within 10 business days if a protocol deviation/violation, or other unanticipated problem.

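### Adverse events are asked about at study visits, which are more frequent in the biofeedback arm, so by-arm counts of minor events are open to unequal ascertainment; separately, Sections 8.3.4 and 8.3.5 state different windows

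*Combined protocol and SAP*

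**What the plan says.** The inquiry rule is in Section 8.3.4: "At each study visit, the investigator will inquire about the occurrence of AE/SAEs since the last visit".

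Section 5.5 describes contact during the intervention period, depending on arm, as "either two times a week for six weeks or once a week for six weeks". Section 6.1.1 gives the biofeedback arm 12 sessions, and Section 4.1 says they are in person. For controls, Section 6.1.1 says: "Three of these visits will be completed in person and three will be completed using an online educational module (6 sessions". It adds: "The online sessions will be completed in week 1, week 3, and week 5". Both arms attend assessments at baseline, week 6 and week 12.

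The Schedule of Activities (Section 1.3) has a single adverse event row for both arms, marked at baseline, in each of weeks 1 to 6 and at both follow-up assessments. It has a weekly activity-level entry for all participants. It puts the pain VAS at three per session for biofeedback and one per week for control.

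Section 6.3 calls the trial open. Section 9.4.4 plans to list or summarise events, and Section 9.4.8 says results will be reported as aggregates for each study group.

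On the window, Section 8.3.4 records events from consent "until 7 (for non-serious AEs) or 30 days (for SAEs) after the last day of study participation". Section 8.3.5 describes the reporting time frame as running "from the initial day of testing as well as the initiation of the biofeedback program through the end of the study".

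**The concern.** When inquiry is tied to visits and the visit schedule is part of the randomised treatment, the arms are asked a different number of times. Minor events such as soreness or short-lived pain are the ones most easily forgotten between askings. The arm asked more often can then show more of them with no true difference.

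Three features of the plan add to this:

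- Section 4.3 already foresees muscle soreness from training.
- The repeated pain score prompts biofeedback participants about the most likely minor complaint at every session.
- Section 8.3.3.2 allows an event to be graded as related on timing alone, so extra asking around exercise sessions could raise attribution as well as counts.

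What is at stake is the tolerability picture that this pilot passes on to the planned multi-center trial.

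The window is a separate question. If two sections define the reporting period differently, staff cannot tell which late events belong in the study's totals.

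**Working it through.** **Inputs.** Two biofeedback sessions a week for six weeks (Sections 4.1, 6.1.1); three in-person and three online control sessions (6.1.1); three assessments in each arm (5.5, 1.3); pain VAS frequency and the weekly adverse event row (1.3).

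**The plan's own figures.** Biofeedback: 2 × 6 = 12 sessions. Control: 3 + 3 = 6 sessions, which agrees with one contact a week for six weeks in Section 5.5. Both are reproduced.

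**Scheduled occasions for asking, by reading of the text.**

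| Reading | Biofeedback | Control | Ratio |
|---|---|---|---|
| Weeks 1–6, online modules count as visits | 12 | 6 | 2.0 |
| Weeks 1–6, in-person visits only | 12 | 3 | 4.0 |
| Whole study, online modules count | 12 + 3 = 15 | 6 + 3 = 9 | 1.67 |
| Whole study, in-person visits only | 12 + 3 = 15 | 3 + 3 = 6 | 2.5 |
| Weekly schedule row taken alone, weeks 1–6 | 6 | 6 | 1.0 |
| Pain VAS during training | 3 × 12 = 36 | 1 × 6 = 6 | 6.0 |

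The weekly row gives a common minimum. It does not remove the additional asking at biofeedback sessions that Section 8.3.4 requires, and it does not say how a control participant is asked in weeks 1, 3 and 5.

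**What this could do to counts (illustration only).** The documents give no recall or event rate. Assume that recall of a minor event decays exponentially with half-life h, and that events fall evenly over the interval L between askings. With k = ln 2 / h, the proportion reported is (1 − exp(−kL)) / (kL). For biofeedback L = 42/12 = 3.5 days; for control L = 7 days (weekly) or 14 days (in-person only).

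| h (days) | L = 3.5 | L = 7 | L = 14 | Ratio to weekly control | Ratio to two-weekly control |
|---|---|---|---|---|---|
| 7 | 0.845 | 0.721 | 0.541 | 1.17 | 1.56 |
| 14 | 0.918 | 0.845 | 0.721 | 1.09 | 1.27 |
| 28 | 0.958 | 0.918 | 0.845 | 1.04 | 1.13 |
| 56 | 0.979 | 0.958 | 0.918 | 1.02 | 1.07 |

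With equal true rates, the ratio of reported events in weeks 1 to 6 would run from 1.02 to 1.56 across these assumptions. From week 6 to week 12 both arms have the same six-week look-back, so whole-study ratios would be closer to 1.

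**Window.** Twelve weeks is 12 × 7 = 84 days. Section 8.3.4 then runs to 84 + 7 = 91 days for non-serious events and 84 + 30 = 114 days for serious ones. If the end point in Section 8.3.5 means the participant's week-12 visit, the two sections differ by 7 and 30 days. If it means the end of the whole trial, Section 8.3.5 runs later than Section 8.3.4 for most participants. The end point is the same for both arms on either reading. Only the start in Section 8.3.5, worded partly around the biofeedback program, has no counterpart for controls.

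**The case against.** The strongest reply is that the schedule already asks everyone weekly. Section 6.1.1 calls all six control sessions visits, Section 5.5 describes weekly contact with the study team, and each inquiry covers the whole time since the previous one, so no calendar time is missed in either arm. No between-arm test of adverse events is planned. Section 8.3.5 also refers the collection procedure to the manual of operations, which is not among the documents and may contain a standard question.

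Much of this stands. It rules out treating 15 against 6 as the only count, and it means the absence of a common question is not proven. It does not equalise the extra session-level asking or the pain scoring, and a descriptive table by group is exposed to the same distortion as a test.

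Three stronger readings are tempting and are not supported:

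- *Event counts cannot be compared between arms.* The documents show a route to unequal ascertainment of minor events, not that all counts are unusable.
- *The wording of Section 8.3.5 loses serious events.* Section 8.3.4 records them to 30 days after participation, and Section 8.3.6 requires expedited reporting of serious events with no end date. Nor is the window in 8.3.5 clearly the shorter one.
- *Control counts will be low by a definite amount.* A reader who assumed 50% to 80% recall after two weeks might infer a 20% to 50% shortfall. That treats biofeedback recall as complete and applies the deficit to the whole study. Keeping complete biofeedback recall in weeks 1 to 6 but allowing equal event rates in the two halves, the shortfall is (1 − p)/(1 + r), where p is two-week and r six-week recall. With r = p it is 0.2/1.8 = 11% to 0.5/1.5 = 33%, still entirely on assumed recall.

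**Conclusion.** The point holds as a minor design weakness. Followed as written, Section 8.3.4 gives biofeedback participants 2 to 4 times as many inquiries as controls in weeks 1 to 6, and 1.67 to 2.5 times as many over the study, depending on whether an online module is a visit. By-arm counts of minor, non-serious events, above all pain and soreness, are therefore open to unequal ascertainment in an open trial. The direction would be toward more reports under biofeedback. The size rests on recall assumptions that the documents do not supply and could be small. Serious events are less likely to be affected because they are harder to forget.

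The window conflict is real but separate: it leaves the study's totals ambiguous and has no bearing on comparability between arms.

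**What to change.** Ask one identical adverse event question once a week in both arms during weeks 1 to 6, attached to the weekly activity-level entry that the Schedule of Activities already requires of all participants. State how it is put to controls in weeks with an online module. Base by-arm adverse event summaries on that question and the three assessments, which makes the weekly inquiries 6 against 6. Keep recording events that come up at sessions, including through the pain score, but show them in a separate listing so that no safety information is lost.

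Separately, reconcile Sections 8.3.4 and 8.3.5 into one window, with a start and an end that apply to both arms and a statement of what is meant by the end of the study.

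The cost is one extra item on an existing weekly form, a second listing and a wording correction. Visits, sessions and sample size do not change.

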8.3.5 ADVERSE EVENT REPORTING

All AEs are collected, analyzed, and monitored by using an Adverse Event Form (MOOP Appendix G). AEs and/or laboratory abnormalities identified in the protocol as critical to participant safety will be reported to the NIAMS and the safety officer. All AEs experienced by a participant during the time frame specified in the protocol (from the initial day of testing as well as the initiation of the biofeedback program through the end of the study) will be reported, as outlined in the protocol (Section 1a of the MOOP).

The procedure for collecting and reporting AEs will be detailed in the following sections. This information will include the role of the Principal Investigator and the Medical Monitor ([name]) in assigning severity and defining the relationship between the AE and the study intervention. A sample AE form can be found in Appendix G. Requirements for reporting AEs to the NIAMS and the study's independent Safety Officer (SO)) is described below.

The Principal Investigator (PI) and study staff members will be responsible for the safety of study participants. It is not anticipated that there will be any significant physical or psychological risks associated with this study. However, federal regulations require prompt reporting to the Virginia Tech Institutional Review Board (IRB), all injuries, adverse events, or other unanticipated problems involving risks to subjects or others that occur in the course of a subject's participation in this research study.

Study team members who become aware of any adverse event related to the study will notify the principal investigator, [name], immediately. Study team members will have contact information for [name] for daytime, evening and weekend hours. If [name] is not available for contact when a study team member becomes aware of a study-related adverse event, [name] or [name], co-investigators on the study, will be contacted. Once [name] (or a co-investigator) is contacted about the adverse event, she / he will make a determination about the reporting requirements in accordance with the Virginia Tech IRB guidelines. This will include notification of the Virginia Tech IRB within 24-hours if a study-related death, within 5 business days if another serious adverse event, and within 10 business days if a protocol deviation/violation, or other unanticipated problem.

The Principal Investigator will report all adverse events and protocol deviations to the study's NAIMS safety officer on a biannual basis, or as requested. The PI or co-investigator will report all serious adverse events to the study's safety officer within 48 hours of the event being made known to the investigator. This immediate report will be followed by a detailed written report as soon as possible.

All adverse events will be collected, analyzed, and monitored in the study's adverse event log, which is kept in the Investigator's regulatory files within a locked file cabinet.

The following definitions from the US Office of Human Research Protections will be used:

Adverse Event (AE): Any untoward or unfavorable medical occurrence in a subject, including any abnormal sign, symptom, or disease, temporally associated with the subject's participation in the research, whether or not considered related to the subject's participation in the research.

8.3.6 SERIOUS ADVERSE EVENT REPORTING

The study clinician will immediately report to the sponsor any serious adverse event, whether or not considered study intervention related, including those listed in the protocol and must include an assessment of whether there is a reasonable possibility that the study intervention caused the event. Study endpoints that are serious adverse events (e.g., all-cause mortality) must be reported in accordance with the protocol unless there is evidence suggesting a causal relationship between the study intervention and the event. In that case, the investigator must immediately report the event to the sponsor.

All serious adverse events (SAEs) will be followed until satisfactory resolution or until the site investigator deems the event to be chronic or the participant is stable. The study sponsor will be responsible for notifying the Food and Drug Administration (FDA) of any unexpected fatal or life-threatening suspected adverse reaction as soon as possible, but in no case later than 7 calendar days after the sponsor's initial receipt of the information.

All serious adverse events (SAEs), unless otherwise specified in the protocol and approved by the IRB and the NIAMS, require expedited reporting by the Principal Investigator to the study's Safety Officer. SAEs will be reported to the Safety Officer and the NIAMS, through the NIAMS contractor within 48 hours of being reported to the Investigator. The immediate reports will be followed by detailed, written reports as soon as possible as follow up information may be required before a written report can be provided. The Principal Investigator will report all serious adverse events to the study's NIAMS safety officer on a biannual basis.

Study team members who become aware of any serious adverse event related to the study will notify the principal investigator, [name], immediately. Study team members will have contact information for [name] for daytime, evening and weekend hours. If [name] is not available for contact when a study team member becomes aware of a study-related adverse event, [name] or [name], co-investigators on the study, will be contacted. Once [name] (or a co-investigator) is contacted about the serious adverse event, she / he will make a determination about the reporting requirements in accordance with the Virginia Tech IRB guidelines. This will include notification of the Virginia Tech IRB within 24-hours if a study-related death, within 5 business days if another serious adverse event.

All serious adverse events will be collected, analyzed, and monitored in the study's serious adverse event log (MOOP Appendix H), which is kept in the Investigator's regulatory files within a locked file cabinet.

